1.1. Problem definition

Introduction

In the past care for people with serious and persistent psychiatric illnesses (SMI) had many shortcomings with regard to the quality and the availability of services. In recent years some promising new services have emerged, mostly in the USA, but their effectiveness in Dutch Mental Health Care has not yet been proven.

Examples include psychosocial interventions such as psycho-education, cognitive behavioral therapy, skills training, peer support, rehabilitation care and interventions supporting recovery. These interventions can help patients to get a better grip on their problems (Illness management) and can promote recovery, but are often not available. Therefore several of these psychosocial interventions are at a basic level included in the program of Illness Management and Recovery (IMR), in Dutch: 'Ziektemanagement en Herstel' or 'Hersteltraining'.

There is some evidence that IMR helps patients to gain control over their illness and to achieve their personal goals (Hasson-Ohayon e.a., 2007; Levitt et al. 2009, Färdig R. et al. 2011).

If desired, subsequent to the IMR program patients receive additional psychosocial treatments. The different parts of the IMR program are not new in Dutch Mental Health Care, but what is new is to offer these services together as an integrated package.

IMR is in line with the goals of patient organizations, which have made recovery a central concept. IMR aims to assist in their goals – to empower patients to take control of their illness and their lives, and work personally for their recovery.

According to Mueser et al. (2002a) IMR is linked to concepts such as recovery, hope, empowerment, personal freedom, cooperation, respect, recognition of the patient as an expert within his own experiences with mental health and 'illness management'.

Phase of implementation of IMR

IMR is currently implemented in several countries. In the Netherlands there is much interest in this type of care. In the Netherlands BavoEuropoort has the most experience with IMR. In some other institutions implementation of IMR is still at the beginning. Mental health care institution 'Rivierduinen' has some experience with IMR (Bovenberg et al 2006, Bovenberg & Staats 2008). In our organisation (BavoEuropoort) from 2009 on, IMR has been implemented on a wider scale (Ebbers 2008), and now 12 groups have completed an IMR course. These groups completed the IMR course after an average period of 12.6 months.

The implementation of IMR at BavoEuropoort has been evaluated with a pilot study, which aims to provide guidelines for an optimal implementation of IMR. This pilot study was also intended as a preparation for the RCT. The report of the pilot will be completed during the course of 2012. Some results are:

- Completers seem to benefit from IMR.
 More women complete IMR
- Completers at baseline score significantly better than non-completers on the IMR-scale client version, IMR-scale clinicians version and on the GAF (psychosocial functioning)
- The fidelity of implementation varies by group and appears to be related to the quality of the trainers.
- The supervision of the trainers needs a substantial boost.
- There is a high rate of drop-out from treatment, especially in the stages prior to the start of the IMR Group.
- The participants who at the start score better on the IMR-scales have a relatively lower drop-out.
- Recruitment of participants in IMR is not easy.
- Given the successful progress of the pilot study it seems that the RCT-study is quite feasible. Data collection in the pilot study went relatively smoothly.

Status of IMR as an Evidence-Based Practice (EBP)

The IMR program was developed in the United States as part of the National Implementing Evidence-Based Practices Project, a major project to implement six evidence-based care programs in the U.S (Drake et al., 2001; Mueser et al., 2003). Other EBP-programs in this project are Assertive Community Treatment (ACT), Integrated Dual Disorder Treatment (IDDT), Individual Placement and Support (IPS), Family Psycho Education (FPE) and Medication Management (MM). With evidence-based we mean that research has given conclusive support that the treatment type is effective.

IMR was based on an empirical review of the research literature on teaching illness selfmanagement strategies to persons with severe mental illness (Mueser et al., 2002). This review identified five empirically supported interventions which were subsequently incorporated into the IMR program: psycho-education, cognitive-behavioral approaches to medication, adherence, teaching relapse prevention, social skills training to improve social support, and coping skills training for persistent symptoms. IMR is named an EBP by the American researchers who have constructed IMR because the ingredients of the program are evidence-based. However, critics have expressed concerns that too many potentially good interventions are given in a short time, with the implication that none of them can be properly implemented (Van der Gaag 2008). For example, to implement cognitive-behavioral therapy (CBT) appropriately, a systematic protocol applied by well-trained staff would be necessary. Moreover critics have pointed to a lack of evidence that social and coping skills programmes are effective. (see the Dutch Multidisciplinary Guidelines for Schizophrenia, 2005). Since this date, however, three RCT's on the overall package of IMR have been executed by Hasson-Ohayon et al (2007), Levitt et al (2009) and Färdig et al. (2011), with positive results for IMR. Despite these positive studies, IMR is not yet broadly accepted as an EBP in Dutch mental health care. In particular, it is mentioned neither in the Dutch multidisciplinary guideline for schizophrenia of 2005, nor in the concept guideline of 2010. More research is needed, especially to investigate whether IMR is effective in the Dutch context.

Theoretical base of IMR

For the theoretical base of IMR is cited from Mueser et al. (2006):

"The IMR program integrates specific empirically supported strategies for teaching illness selfmanagement into a cohesive treatment package based on 2 theoretical models: the transtheoretical model and the stress-vulnerability model.

The trans-theoretical model proposes that motivation to change develops over a series of stages (pre-contemplation, contemplation, preparation, action, maintenance) and that facilitating change requires stage-specific interventions (Prochaska & DiClemente 1984; Prochaska 1984). At the earliest stages, people are not committed to change and intervention focuses on instilling motivation. In the IMR program, motivational interviewing (Corrigan et al. 2001; Miller & Rollnick 2002) is used at the beginning and throughout the program to help clients develop their own vision of recovery, to identify and pursue their personal goals based on that vision, and to explore how improved illness management can help them achieve these goals.

The stress-vulnerability model (Liberman et al. 1986; Zubin & Spring 1977) posits that the course and outcome of schizophrenia is determined by the dynamic interplay of biological vulnerability, stress, and coping. IMR is aimed at interrupting the cycle of stress and vulnerability that leads to relapse and poor functioning (see figure 1). In IMR, the proximal goal is to teach clients the fundamentals of illness self-management based on the stress-vulnerability model (ie, adherence to medications, reduced substance use, increased social support, increased coping, involvement in meaningful activities) in order to improve illness outcomes such as symptoms, relapses, and hospitalizations. Then, through the combination of pursuing personal goals and improved illness self-management, the distal goal of IMR is to help clients make progress toward recovery, including objective (e.g. community functioning, social relationships, work) and subjective (e.g. sense of purpose, hope, confidence) dimensions."

Conceptual Framework for the Illness Management and Recovery program

[figure not shown]

Figure 1 source: (Mueser et al. 2006)

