5.3 Sample Size

Based on the effect sizes of the studies of Hasson et al. (2007) with 210 participants (.41, Cohen's d), Levitt et al. (2009) with 104 participants (.36) and Färdig et al. (2011) with 41 participants (.60) we expect a medium effect size of 0.40.

Based on the power analyses with three moments of measurement (mixed models) and equal allocation to experimental and control group, a power of .80, correlation between measures .50, alpha at 0.05 and an effect size of .40, we need to randomize 148 patients, 74 to the experimental condition and 74 to the CAU-group (see Twisk (2003) and Guanghan L. and Kung-Yee L. (1997).

Because of the (conservatively estimated) expected drop-out from treatment in the experimental condition of 50% we choose to allocate more patients to the experimental (IMR-) condition than to the CAU-group (proportions of 3:2). Then we need to randomize 185 patients, 111 patients to the experimental condition and 74 to the CAU-group.

Because we expect a total drop-out in each group from measurements of 8 % we need 80 patients in the control condition and 120 patients in the experimental condition. In total: 200 patients (see Annex 1).

6. Intervention

The average duration of the total IMR-training is 12 months. The IMR-training consists of 11 modules that are given weekly. The first module is given individually. During this individual module the patients decide which goals they want to work on during the program.

Then the patients join an IMR group for the other modules. Each module takes about 3 to 4 sessions of one and a half hours each. The IMR group is guided by two trainers (psychiatric nurses). The trainers received a two-day course in IMR and attend supervision once every two weeks.

The modules are described in the IMR-workbooks, translated into Dutch, which the patients received. If necessary, the original American text is adapted to the Dutch context. The modules are: 1. Recovery Strategies, 2. Practical Facts about Mental Illness, 3. Stress-Vulnerability Model, 4. Building Social Support, 5. Using Medication Effectively, 6. Alcohol and Drugs Use, 7. Reducing Relapses, 8. Coping with Stress, 9. Coping with Problems and Persistent Symptoms, 10. Getting Your Needs Met in the Mental Health System, 11. Health for you.

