8.1.3. Exploratory analysis

The pilot study showed that women significantly more often are IMR completers and that completers at baseline scored better on the IMR-scales and on the GAF (psychosocial functioning). This makes it interesting to examine whether women benefit more from IMR than men and whether patients who at baseline score higher in terms of illness management, psychosocial functioning and symptoms, improve more than patients who at baseline score lower on these domains. Earlier IMR research was often focused on patients with psychotic disorders. We want to investigate whether the effect varies by diagnosis group. We are able to explore this because in the IMR-training of Bavo Europoort chronic patients with various diagnoses participate. Since half of the population of outpatients of Bavo Europoort has an immigrant background, we would like to explore whether IMR for participants from ethnic minorities is as effective as for participants of native background.

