8.2.4. Research data

Data on primary, secondary and tertiary outcome measures and the mediating factors will be collected at baseline (before randomization), after the IMR-training (from 9 to 12 months) and during follow-up (after 15 - 18 months). The interviewers will be blind for the (experimental or control) condition of the patient. For the recruitment of participants and data collection, students will be employed.

During the first contact (at baseline) and after the patient has given informed consent, the research interview will take place and the interviews will be conducted. Subsequently randomization will take place. Each assessment will last up to 80 minutes. If desired, the interview will take place on two occasions. The assessments will be done at the location where the patient usually comes. Besides the previously mentioned outcome measures and mediating factors at baseline the following data will also be collected:

- Demographic data: age, sex, living situation, source of income, education level, country of birth of the patient and of his father and his mother.

- Consumption of mental health care: number of outpatient contacts, number of crisis contacts, number of admissions and the number of compulsory admission orders (total and in the last two years) during the past two years before and after moment of measurement 1.
- Psychiatric diagnosis: DSM-IV-TR diagnosis (five axes) according to the clinician. We realize that this is not always reliable, but it is not possible with the resources available to do a standardized diagnostic interview.

The analysis will be based on the intention to treat principle. Data will be collected of patients who drop out of the IMR program. Based on the pilot study, during the IMR intervention, 50 % drop out from IMR is expected. In order to do analyses related to generalizability of the study, the demographic characteristics of all patients who refused to participate will be registered, as well as the characteristics of the patients who drop-out from the study.

The demographic variables, consumption of mental health care and psychiatric illness will be collected by the researcher from the administration of the institution, supplemented by data from the file.

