8.4 Participating sites

The following IMR-teams (teams for outpatient care)/ locations within BavoEuropoort will participate in the study:

IMR Team Noord Oudedijk (Rotterdam)

IMR Team, Oost Oudedijk (Rotterdam)

Time-out Team Carnissesingel (Rotterdam)

IMR Team Zuid Carnissesingel (Rotterdam)

IMR Team Centrum Westblaak (Rotterdam)

IMR Team Zuid-Hollandse Eilanden (Spijkenisse).

9 Statistics

- For measurement of the effects of the IMR-training on the primary outcome measure, and on secondary outcomes on three moments of measurement we use Linear Mixed Models.

Differences in time between groups can be examined with cross level interaction for time x group interaction effect.

- The groups are compared at the final and follow-up assessments in terms of a main group effect, to test the question whether the groups differ after treatment, controlling for baseline.
- For validation of the scores on the primary outcome measure on different aspects of Illness Management (Stress, Social Support, Medication adherence, Drugs use, Symptoms/Remission/Relapse, Coping) we use multiple regression analysis, logistic regression analysis and multinomial analysis.

'For prediction of the effect on the primary outcome measure using the baseline data in terms of functioning (scores on IMR-scales, GAF-scores, Social Functioning Scale and BSI) we use linear regression analysis.

For prediction of the effect on the primary outcome measure using the baseline data in terms of patient characteristics (gender, etnicity, diagnosis) we use t-tests and one way ANOVA.'

If we find effects of the IMR-training on the Distal outcome measures of recovery:
 to determine the influence of Illness management aspects as mediating factors on the effects on recovery we use Multiple Mediator Analysis for SPSS (Preacher & Hayes, 2008).

10 Feasibility of the study

The organization of the IMR training and the organization and logistics of the research require a major effort by Bavo Europoort and the research team.

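### The primary model names no adjustment beyond baseline; pre-specifying sex and baseline GAF would add modest precision and a safeguard against selective loss

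*Protocol*

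**What the plan says.** Section 9 (Statistics) uses linear mixed models over three measurements. It compares the groups at the final and follow-up assessments "to test the question whether the groups differ after treatment, controlling for baseline". No other covariate is named for this comparison, not even diagnosis (psychotic disorder yes or no), on which section 4 stratifies the randomisation.

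On the pilot, section 1.1 reports: "Completers at baseline score significantly better than non-completers on the IMR-scale client version, IMR-scale clinicians version and on the GAF (psychosocial functioning"). Section 8.1.3 adds: "The pilot study showed that women significantly more often are IMR completers".

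Both variables are available at baseline. Sex is among the demographic data in section 8.2.4. Section 9 lists GAF scores among the baseline data, and section 8.2.4 records "Psychiatric diagnosis: DSM-IV-TR diagnosis (five axes) according to the clinician", which is presumably their source. Section 9 uses them only in separate analyses of what predicts the effect on the primary outcome: GAF in a linear regression, and gender in t-tests or one-way ANOVA.

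**The concern.** A likelihood-based mixed model handles missing outcomes well when the loss depends only on what the model contains: here group, time, the baseline score and any earlier follow-up score. If loss also depends on sex or GAF, and these predict the outcome beyond what the model holds, the comparison can shift. The pilot links both variables to staying in the course, and only one arm has a course to leave.

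The second stake is precision. If sex and GAF are prognostic, leaving them out puts explainable variance into the error term, although the data are already collected.

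**Working it through.** **1. Reproduce the plan's own figure.** Section 5.3 assumes "three moments of measurement (mixed models) and equal allocation to experimental and control group, a power of .80", with "correlation between measures .50, alpha at 0.05 and an effect size of .40, we need to randomize 148 patients". Sidedness is not stated.

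n per arm = 2(1.96 + 0.8416)² V / d², with d = 0.40. For the mean of two post-baseline measures at correlation 0.50, V = (1 + 0.5)/2 = 0.75. One follow-up adjusted for baseline gives the same value, 1 - 0.5² = 0.75.

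n = 2 × 7.849 × 0.75 / 0.16 = 73.6, so 74 per arm and 148 in total. This matches the protocol. One-sided alpha would give 58 per arm, so two-sided is the reading that fits. The sample size is not in question.

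**2. Precision without the covariates.** At 111:74, SE = √[0.75(1/111 + 1/74)] = 0.130. Power = Φ(0.40/0.130 - 1.96) = 0.868.

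**3. Precision with sex and GAF.** V becomes 0.75(1 - R²), where R² is the share of residual variance they explain beyond the baseline score. The protocol gives no value, so R² is an assumption. The SE falls by 1 - √(1 - R²).

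| Assumed R² | SE at 111:74 | SE reduction | Power |
|---|---|---|---|
| 0 | 0.130 | 0% | 0.868 |
| 0.02 | 0.129 | 1.0% | 0.875 |
| 0.05 | 0.127 | 2.5% | 0.884 |
| 0.10 | 0.123 | 5.1% | 0.900 |
| 0.20 | 0.116 | 10.6% | 0.931 |

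I take 0.02-0.10 as the working range. Zero cannot be excluded.

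**4. Planned loss.** Section 8.2.1 expects at least 111 of 120 and 74 of 80 patients at follow-up. Both ratios are 0.925, so 7.5% is lost in each arm, in line with the 8% of section 5.3.

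**5. Bias if loss is selective in the IMR arm only.** This is a large-sample simulation (1,000,000 patients, true effect 0, outcome SD 1, 3:2 allocation, one follow-up). All of the following are assumptions:
- The correlation is 0.5 between baseline and outcome, and 0.4 between GAF and baseline score.
- Control loss is random at 8%.
- IMR-arm loss follows a logistic model in baseline score, sex and the part of GAF not explained by the baseline score, at two strengths (coefficients 0.7 and 1.5).
- The outcome slopes b, for sex and for that part of GAF, are both 0.1, 0.2 or 0.3. This gives R² = (b² + 0.25b²)/0.75 = 0.017, 0.067 or 0.15.

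| IMR-arm loss | Bias towards IMR, baseline only (SD) |
|---|---|
| 8% | 0.008 to 0.034 |
| 25% | 0.016 to 0.090 |
| 50% (every expected course drop-out unmeasured) | 0.037 to 0.169 |

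With sex and GAF in the model, the bias was within 0.006 SD of zero throughout. That is by construction, because the simulated loss depends only on variables then in the model.

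For scale, 0.034 is about a quarter of the standard error of 0.130, and 0.090/0.40 = 22.5% of the planned effect.

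**The case against.** A reader might infer from the pilot that lower-functioning IMR patients will be missing at the later measurements and that the result will therefore favour IMR. The protocol does not support this. The pilot results describe who completes the course, not who is measured. Section 8.2.1 keeps leaving the course separate from leaving the study. Section 8.2.4 sets intention to treat and collects data from patients who stop IMR. Section 5.3 expects 50% treatment drop-out but only 8% measurement loss in each group. This objection stands.

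Further points on that side also stand, in whole or in part:
- The patient-rated IMR scale is among the pilot predictors of completion, and its baseline value is already in the model. Part of any selection is therefore handled. The planned model would also use the second measurement of patients who miss only the third, which the one-follow-up simulation does not.
- Predicting completion, or a different response to treatment, is not the same as predicting outcome. The precision gain may be nil.
- If both arms lost similar patients, the shifts would largely cancel.
- GAF has no row in Annex 3 and appears to come from clinician diagnosis, which section 8.2.4 concedes is not always reliable. Some values may be missing.
- An analysis plan that is not shown may list more covariates, and section 9 excludes none.

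What remains is that section 9 does state an adjustment, and a better one is available from data in hand. The 8% is also an expectation. Section 1.2.1 cites 19% and 12% drop-out by arm in one earlier IMR trial, and 29% overall in another with no split by group. The protocol does not say how much of this was loss to measurement. A control arm has no IMR course to leave, however, so measurement loss above 8% and unequal between arms is plausible.

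**Conclusion.** The point holds as a modest improvement to a stated method. It does not show an error in the sample size or a demonstrated bias.

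The benefit is a standard error lower by about 1-5% if sex and GAF explain 2-10% of the residual variance, and none if they are not prognostic. The covariates also act as a safeguard if measurement loss exceeds 8% or follows drop-out from IMR.

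Under the assumed selective loss confined to the IMR arm, the bias avoided is about 0.01-0.03 SD at the planned loss and 0.02-0.09 SD at 25% IMR-arm loss. The largest figures, up to 0.17 SD, need every patient who leaves the course to go unmeasured as well, which the protocol plans against. They should not be read as an expected bias.

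**What to change.** In section 9, pre-specify sex and baseline GAF as fixed effects beside the baseline patient-rated IMR score in the primary mixed model. Add the diagnosis stratum used at randomisation (section 4). Keep patients with a missing baseline GAF in the model by simple baseline imputation, for example the mean over both arms combined, without using allocation or outcome.

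The cost is a sentence or two in section 9, three extra parameters with 200 patients randomised, and the handling of missing clinician-recorded GAF. No new data collection is needed. Fixing the list before outcome data are seen also removes a later choice of covariates.

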1.2 Relevance

1.2.1 Strengthening demand-orientation

What are the main elements of IMR?

Illness Management and Recovery (IMR) is a program of care in the form of a training course for patients with severe and persistent psychiatric problems, based on a combination of different types of interventions focused on recovery. The idea underlying the training course is that the patient learns to gain control of his illness (illness management) and to make appropriate choices based on accurate information and skills training.

IMR can be described as a structured training program for people with severe and persistent mental illness which helps to:

- Set meaningful personal goals
- To gather information and acquire skills to achieve a greater degree of control over the psychiatric illness.
- To work on recovery.

IMR is based on a review of controlled research (Mueser et al 2002a) in which five types of interventions (Mueser et al call them 'strategies') emerged which were incorporated into the training program.

These include psycho-education, cognitive behavioral approaches to improve medication compliance (medication management), relapse prevention by developing a crisis plan, strengthening social support with training in social skills and training to learn skills to cope with persistent symptoms (coping skills training).

To motivate patients to learn how to deal better with their disease and to make progress in their lives, IMR begins with an exploration of the meaning of recovery for the patient and the setting of personal recovery goals that can be worked on during the training course. The program includes 11 modules (see 6. Intervention).

It is intended that patients follow all modules. The total duration of the training program is on average one year, but the duration varies, depending on the frequency of sessions and the number of sessions per module. IMR may be offered individually or in a group format.

The importance of recovery

Anthony et al. (2003) introduced the term 'recovery' as a new and complementary approach to the rehabilitation process. According to Anthony, recovery includes much more than regaining mental health. The patients must also get over the stigma, the traumatic effects of certain practices, the lack of opportunities to shape their lives and the lost perspective on the future. According to Anthony the term means: "recovering the sense of self, again entering into a relationship with other people, converting powerlessness to power, giving new meaning to life and the retrieval of hope".

In the Netherlands the patient movement headed by Wilma Boevink has adopted the term "herstel" (recovery). Boevink (2002) says "recovery is something that patients do themselves. It is a search for how to deal with mental health problems, how to get a grip on the problems and how to put life increasingly in your own hands. Recovery is much more than cure."

Bond et al. (2005) noted that in the Netherlands there is too much emphasis on crisis intervention and stabilization of the patient. He advises investing in a recovery oriented approach. In his opinion, patients have more capabilities if they are well informed and facilitated. According to Bond elements of a recovery orientation are an active collaboration with the patient to reach his personal goals, the propagation of a consistent message of hope and optimism at each contact, giving priority to the choice of the patient in all aspects of the treatment, housing, work and medication, and emphasize the strength of the patient.

In their review of the research, Mueser et al. (2002a) say that recovery refers not only to relief from symptoms but also to social success and personal accomplishment in areas that the person defines as important. According to their paper recovery has been conceptualized as a process, as an outcome, and as both. What they call critical about recovery is the personal meaning that each individual attaches to the concept. Common themes of recovery, which they name, are the development of self-confidence, of a self-concept beyond the illness, and of a sense of well-being, hope, and optimism. Recovery has therefore to do with empowerment, perceived self-stigma and setting and achieving of meaningful goals.

Dröes & Plooy (2010) distinguish three different areas of recovery: recovery from illness, recovery of individual roles and recovery of personal identity. In the study by Bogaards et al (Bogaards et al. 2010, Oosterbaan et al. 2011) a fourth area is added: recovery of daily functioning.

Illness Management

Mueser et al. (2002a) define illness management as 'professional-based interventions designed to help people collaborate with professionals in the treatment of their mental illness, reduce their susceptibility to relapses, and cope more effectively with their symptoms'. Illness management means that the patient takes control over his illness and learns to intervene to prevent relapse. The patient learns too to (re) influence his social environment and to find his way to the appropriate care. The main goal of IMR is to offer people the right information and skills to allow them to make for themselves the right choices in their treatment. In this way IMR moves to meet the needs of the patient movement. The care provider tries to support the recovery process of the patient (together with his friends/family) and to help the patient to fulfill his role as a citizen.

Mueser et al. (2002a) call it critical to peoples' developing hope for the future to formulate personal recovery goals to help them to gain mastery over their symptoms and relapses. Basic education about mental illness facilitates their ability to regain control over their lives and to establish more collaborative and less hierarchical relationships with professionals.

The care professional takes on a less dominant position and the patient, and his or her peer group have space to work together with professionals to optimize the treatment.

This fits well with the ideas of Boevink (2002): "integration of Mental Health Care has no chance of success if only the services integrate into society".

Equally important is that the people who use these services change their identity of psychiatric patient to that of participants in society. "Mueser et al. (2002a) describe the advantages of IMR as: "Illness management is a broad set of strategies designed to help individuals with serious mental illness collaborate with professionals, reduce their susceptibility to the illness, and cope effectively with their symptoms. Recovery occurs when people with mental illness discover, or rediscover, their

strengths and abilities for pursuing personal goals and develop a sense of identity that allows them to grow beyond their mental illness".

Mueser et al (2002a) say that illness management and recovery are closely related, with illness management focused primarily on minimizing people's symptoms and relapses and recovery focused primarily on helping people develop and pursue their personal goals.

Drop-out

IMR is a relatively long-term care program (at least nine months at one session per week) for chronic psychiatric patients, usually involving starting of group sessions after completing the first individual module. Various publications and our own experience show that in different phases of the IMR program relatively high drop-out from treatment occurs. The overall drop-out in the IMR study of Hasson-Ohayon et al (2007) was 29% (60 out of 210; there is no indication of how this is split between the two research groups). The overall dropout rate in the study of Levitt et al (2009) (executed in a supported housing setting) was 15% (intervention group: 19%, control group: 12%). During the visit in 2009 of some staff members of BavoEuropoort to the U.S., it appeared that in Manchester (NH), there was 50% dropout from treatment of patients of ACT teams who participated in an IMR training. The drop-out from treatment in the pilot-study of Bavo Europoort from the moment of starting Module 1 was 44% (32 of 72, there were 40 completers, i.e. 56%).

